3.2 Dosing Regimen

Each treatment solution will be prepared by an unblinded designee(s) who is otherwise not involved in study participation after the treatment injection. The health care professional administering the injection will be unblinded to the treatment administered. All other study staff, as well as each study subject, will be blinded to study therapy until the end of the study. Eligible subjects will be randomized to receive 1 of 3 treatments:

- Rexlemestrocel-L alone: One injection of approximately 6 million rexlemestrocel-L cells in freeze media mixed in a 1:1 by-volume ratio with saline. A vial with 2mL of thawed rexlemestrocel-L cells and freeze media will be mixed with 2mL of saline. Two milliliters of the resulting mixture will be injected via pressure manometer syringe into the nucleus pulposus of the index level.
- Rexlemestrocel-L + HA: One injection of approximately 6 million rexlemestrocel-L cells in freeze media mixed in a 1:1 by-volume ratio with 1% hyaluronic acid (HA) solution. A vial with 2mL of thawed rexlemestrocel-L cells and freeze media will be mixed with 2mL of 1% HA solution. Two milliliters of the resulting mixture will be injected via pressure manometer syringe into the nucleus pulposus of the index level; OR
- Saline: One injection of 2mL of thawed saline from one vial will be mixed with 2mL of thawed saline from another vial of saline. Two milliliters of the resulting saline mixture will be injected via pressure manometer syringe into the nucleus pulposus of the index level.

Treatment assignment will occur in sequential chronological order according to a central master list of random assignments. Randomization will be stratified

CONFIDENTIAL

3.3 Study Sites

In order to enroll approximately 360 subjects, up to 45 study centers in the US, Australia, and potentially the EU will participate.

4. STUDY ANALYSIS SET

4.1 Overview

This study will enroll approximately 360 subjects in the randomization ratio of 1:1:1. Eligible subjects will be those with a history of chronic (> 6 months) low back pain not adequately controlled by conservative measures and associated with moderate radiographic degenerative changes of a disc in the lumbar spine from L1 to S1.

4.2 Eligibility Criteria

4.2.1 Inclusion Criteria

Subjects who meet the following criteria will be included in the study:

- 1. Male and female subjects 18 years of age and older
- 2. If female of childbearing potential, subject is non-pregnant, non-nursing, and agrees to use highly effective methods of contraception for a minimum of 24 months post-treatment (if a subject becomes pregnant during the study, the subject will remain in the study and only the requirement for radiation (x-ray or MRI) should be removed)
- 3. Signed informed consent and country-appropriate privacy forms (e.g., HIPAA forms in the US) indicating subject is willing to undergo treatment and willing to be available for each examination scheduled over the study duration
- 4. Have documented diagnosis of moderate radiographic degeneration of an intervertebral disc from L1 to S1, with a disc suspected of causing CLBP

Chronic low back pain associated

with moderate radiographic degeneration at a lumbar disc is defined as the following (subject must meet all of the listed conditions):

- a. Chronic low back pain for at least 6 months
- b. Have failed 6 months of conservative back pain care. (Conservative treatment regimens may include any or all of the following: initial rest, medications [e.g., anti-inflammatory, analgesics, narcotics/opioids, muscle relaxants], massage, acupuncture, chiropractic manipulations, activity modification, home-directed lumbar exercise program, and non-invasive pain control treatments or procedures)
- c. Have at a minimum undergone supervised physical therapy, such as daily walking routines, therapeutic exercises, and back education programs specifically for the

treatment of low back pain *AND* taken a pain medication for back pain (e.g. NSAID and/or opioid medication)

- d. Change from normal disc morphology of the index disc as defined by radiographic evaluation by the core imaging evaluation provider. Radiographs must show all of the following:
 - i. A modified Pfirrmann score of 3, 4, 5 or 6 on MRI at the index disc as determined by radiographic core lab
 - ii. Modic Grade II changes or less on MRI at the index disc as determined by radiographic core lab
 - iii. With or without contained disc protrusion at the index disc on MRI as determined by radiographic core lab
- e. Low back pain of at least 40mm and not more than 90mm of 100mm on low back pain VAS (average pain over 24 hours)
- f. Leg pain \leq 20mm in both legs on a 100mm VAS scale
- g. ODI score of at least 30 and no more than 90 on a 100 point scale.

4.2.2 Exclusion Criteria

Subjects will be excluded from participating in the study if they meet any of the following exclusion criteria:

- 1. Female subjects who are pregnant or nursing, or women planning to become pregnant in the first 24 months post-treatment (if a subject becomes pregnant during the study, the subject will remain in the study and only the requirement for radiation (x-ray or MRI) should be removed)
- 2. Extreme obesity, as defined by NIH Clinical Guidelines Body Mass Index (BMI > 40)
- 3. Have undergone a surgical procedure (e.g. discectomy, intradiscal electrothermal therapy, intradiscal radiofrequency, artificial disc replacement, interbody fusion) on the disc at the index or adjacent level
- Osteoporosis, as defined by dual-energy X-ray absorptiometry (DEXA) scan. A DEXA T-score of ≤ -2.5 will exclude the subject. Only the following at-risk subjects will be required to undergo a DEXA scan at screening:
 - a. Female subjects with a Simple Calculated Osteoporosis Risk Estimation (SCORE) of ≥6 and male subjects with a Male Osteoporosis Risk Estimation Score (MORES) of ≥6
 - b. Females ≥50 years of age or who are post-menopausal or post-hysterectomy with oophorectomy
 - c. Subjects taking bisphosphonate medications for the treatment of osteoporosis

- d. Subjects with a history of chronic, high-dose steroid use (oral and/or inhaled). High-dose steroid use is defined as:
 - i. Daily, chronic use of oral steroids of $\geq 5 \text{ mg/day}$
 - ii. Daily, chronic use of inhaled corticosteroids (at least twice per day)
 - iii. Use of short-term (less than 10 days) oral steroids at a daily dose >20mg prednisone (or equivalent) within 1 month of study procedure
- 5. Any lumbar intradiscal injection, including steroids, into the index or adjacent discs prior to treatment injection, with the exception of the following injections performed at least 2 weeks prior to study treatment:
 - a. Contrast medium (discography or other diagnostic injection)
 - b. NSAIDs
 - c. Nerve-blocking anesthetics (e.g., lidocaine, bupivacaine)
 - d. Antibiotics
 - e. Saline
- 6. Have undergone a procedure affecting the structure/biomechanics of the index disc level (e.g. posterolateral fusion)
- 7. Epidural steroid injections within 8 weeks prior to treatment injection
- Have received chronic (more than 7 consecutive days) treatment with systemic corticosteroids at a dose equivalent to prednisone ≥ 10 mg/day within 14 days prior to injection procedure
- 9. Have a known history of hypersensitivity or anaphylactic reaction to murine or bovine products or dimethyl sulfoxide (DMSO)
- 10. Have a known history of hypersensitivity or anaphylactic reaction to hyaluronic acid (HA)
- 11. Active malignancy or tumor as source of symptoms or history of malignancy within the 5 years prior to enrolment on study, except history of basal cell carcinoma of the skin, squamous cell carcinoma of the skin, or squamous cell carcinoma of the cervix if fully excised and with clear margins
- 12. Currently participating in another investigational trial and/or plans to participate in any other allogeneic stem cell/progenitor cell therapy trial within 36 months after study treatment
- 13. Have been a recipient of prior allogeneic stem cell/progenitor cell therapy for any indication or autologous stem cell/progenitor cell therapy or other biological intervention to repair the index intervertebral disc
- 14. An average baseline morphine equivalent dose (MED) of >75mg/day as determined by ediary entries during the screening period

- 15. Taking systemic immunosuppressants
- 16. Current infection or prior history of spinal infection at the index level (e.g., discitis, septic arthritis, epidural abscess) or an active systemic infection
- 17. Pain catastrophizers, defined as having a score of 30 or more on the Pain Catastrophizing Scale
- 18. A medical condition, serious intercurrent illness, or extenuating circumstance that would preclude participation in the study or potentially decrease survival or interfere with ambulation or rehabilitation. Examples of conditions that should be excluded are as follows:
 - History of transient ischemic attack (TIA)
 - History of Stroke
 - Uncontrolled diabetes
 - Autoimmune disease (only if they interfere with ambulation or rehabilitation)
 - Muscular dystrophy
 - Rheumatoid arthritis
 - Active liver disease
 - Upper motor neuron disease
 - Myelopathy
 - Disorders of bone metabolism (osteomalacia or Paget's disease)
- 19. Cauda equina syndrome
- 20. Subjects involved in spinal litigation, including workman's compensation, unless litigation is complete
- 21. Currently incarcerated (prisoners)
- 22. Are transient or have a severe alcohol or substance abuse problem defined as answering yes to 6 or more symptoms on the DSM-5 alcohol or substance/opioid questionnaires
- 23. Unable to complete all required e-diary entries, assessments and follow-up according to the protocol.
- 24. A history of mental illness/incompetence. Mental illness/incompetence is defined as meeting the following criteria on the DSM-5 Self-Rated Level 1 Cross Cutting Symptom Measure – Adult questionnaire
 - Domain 1, Depression A response of 4 on either question
 - Domain 6, Suicidal Ideation A response of 4 on the question
 - Domain 7, Psychosis A response of 1 to 4 on either question
 - Domain 9, Memory A response of 4 on the question

- 25. Have a serious intercurrent medical condition or any other conditions or social situations that would impair the ability to give informed consent or unacceptably reduce protocol compliance or safety of the study treatment.
- 26. Body habitus precluding adequate fluoroscopic visualization for the procedure or the procedure is physically impossible due to inability to inject the nucleus pulposus
- 27. Presence of ferromagnetic implants that would disallow MRI of the index disc
- 28. Presence of neurologic deficit on any component of the lumbar neurological exam at baseline (i.e., motor, sensory, or reflex portion of the exam)
- 29. A positive screen for human immunodeficiency virus (HIV) by antibodies or nucleic acid test
- 30. Clinically significant nerve pain (e.g., chronic radiculopathy or neuropathy)
- 31. Clinically significant sacroiliac joint pain based on the Appropriate Use Criteria established by the Spine Intervention Society including a targeted, pre-specified physical examination, and, if deemed medically necessary, confirmed by anesthetic injection. If a previously performed anesthetic injection to confirm SI joint pain was performed up to 6 months prior to injection (with documentation indicating that the SI joint pain is not the source of the subject's pain), this does not need to be repeated at screening.
- 32. Compressive pathology due to stenosis or disc protrusion on MRI with associated clinical symptoms defined as leg pain VAS > 20mm out of 100mm or neurologic deficit on neurologic exam
- 33. Disc extrusion with a maximum dimension greater or equal to twice the posterior height of the disc, or disc sequestration in the lumbar spine on MRI as determined by radiographic core lab
- 34. This criterion left blank on purpose
- 35. Modified Pfirrmann score of 7 or 8 at any lumbar level on MRI evaluation as determined by the core imaging provider
- 36. Symptomatic involvement of more than one lumbar disc (i.e. more than one level with concordant pain upon provocative discography, if performed)
- 37. Symptomatic central vertebral canal stenosis as defined by neurogenic claudication
- 38. Spondylolisthesis or retrolisthesis Grade 2 and above (>25% of the AP dimension of the superior endplate of the inferior vertebrae) at the index or adjacent level(s) on radiographic evaluation as determined by radiographic core lab or Spondylolysis at the index or adjacent level(s).
- 39. Lumbar spondylitis or other undifferentiated spondyloarthropathy affecting the index disc.

- 40. Spinal deformity defined as lumbar scoliosis with a Cobb angle of the lumbar spine greater than 15 degrees on radiographic evaluation as determined by radiographic core lab.
- 41. An acute fracture of the spine at the index or adjacent levels that has not healed, or clinically compromised vertebral bodies at the index level due to current or past trauma (e.g. sustained pathological or multiple fractures of vertebrae.
- 42. Facet pain at the index level or adjacent segments as determined by a diagnostic medial branch block (a facet block injection is not acceptable for making this determination) to rule out facet joint involvement. If a previously performed medial branch block was performed up to 6 months prior to injection (with documentation indicating that the facet joint is not the source of the subject's pain), this does not need to be repeated at screening.
- 43. Have not completed a minimum of 10 out of 14 daily e-diary entries of pain medication use (e.g. NSAID, aniline analgesics and opioid use) prior to screening injection procedures (i.e., diagnostic disc injection to confirm intact annulus, discography, medial branch block and SI joint injection, if deemed necessary). If a historical screening injection procedure is used, the e-diary pain medication usage collection should be completed at least 14 days after the screening procedure.
- 44. Full thickness annular tears in the index level as determined by free flowing contrast media through the annulus fibrosis. Injection of contrast media into the index level must take place at least 2 weeks prior to the treatment injection. If a previously performed discography with contrast was performed up to 6 months prior to injection (with documentation indicating no full tear of the disc), this does not need to be repeated at screening.

4.3 Information to be collected for Screen Failures and Randomized Not-treated Subjects

Subjects who fail any inclusion/exclusion criteria up to the timepoint of randomization are considered screen failures. Subjects who are randomized but do not receive treatment are considered randomized not-treated subjects.

The following information must be recorded for all screen failures and randomized not-treated subjects: demography, medical history, concomitant treatment, inclusion/exclusion criteria met and not met, adverse events, if any, and reason for screen failure or withdrawal. If diagnostic injection for confirmation of full thickness annual tears was performed, information regarding the procedure will also be collected.

4.4 Re-screening

Screen failures may be re-screened **twice** at the discretion of the investigator (however, subjects who have been previously randomized cannot be re-screened). Subjects will be assigned a new study identification number upon re-screening. All screening activities will need to be repeated with the possible exception of the following, if performed within the permitted timeframe: diagnostic medial branch block; diagnostic injection to confirm intact annulus or discography; possible anesthesia injection for detection of SI joint point, anterior/posterior (AP), lateral and flexion-extension X-rays; and screening MRI. For these screening activities to be waived (i.e., not repeated), they must have been performed within the following timeframes:

Screening injection procedures:

- **Diagnostic medial branch block**: within 6 months prior to injection of study treatment (with documentation indicating no clinically significant facet pain in accordance with exclusion #42)
- SI joint injection to determine SI joint pain (not required for all subjects): within 6 months prior to injection of study treatment (with documentation indicating no clinically significant SI joint pain in accordance with exclusion #31)
- **Diagnostic injection to confirm intact annulus or discography**: at least 2 weeks but no longer than 6 months prior to injection of study treatment.

Imaging:

- MRI: within 6 months prior to injection of study treatment
- **DEXA:** within 6 months prior to injection of study treatment
- **AP, lateral and flexion-extension x-rays:** within 6 months prior to injection of study treatment and according to study-defined procedure.

Note: MRIs and X-rays should be taken on the same machine using the same settings, and in accordance with the radiographic guidelines provided, from baseline to completion of the study to minimize potential differences in results caused by use of different machines. Radiographic evaluations may vary for a given subject depending on the time of day the assessments are made. Therefore, for each subject, all radiographic evaluations of a specific type (e.g., X-ray) should be taken at the same time of day at each assessment if possible, preferably in the morning.

If the diagnostic injection to confirm an intact annulus or discography is repeated in re-screening, a neurological exam must be performed prior to the injection procedure and again after the procedure. If a recent diagnostic injection taken before the screening period serves as the

baseline evaluation for a subject, the pre-injection neurological exam may be waived, though a neurological exam will need to be performed prior to any additional invasive procedures or the treatment injection. This post-diagnostic injection neurological exam will be used as the subject's baseline neurologic status.

For subjects who are re-screened, the following patient-reported outcomes must be repeated no sooner than 2 weeks after the most recent diagnostic injection procedure to confirm an intact annulus or discography: VAS assessments (leg and low back pain), ODI questionnaire, EQ-5D, iPCQ, and e-diary collection of pain medication usage for a minimum of 10 out of 14 days.

4.5 Subject Withdrawal

Subjects will be free to withdraw from the study at any time, for any reason.

A subject also may be withdrawn/removed by the investigator, if necessary, to protect the subject's health. The investigator has the right to withdraw subjects from the study in the event of intercurrent illness, adverse events, administrative, or other reasons. Any reasons for withdrawal must be documented and explained to the subject.

It is understood, however, by all concerned, that an excessive rate of withdrawals can render the study uninterpretable. Therefore, unnecessary withdrawal of subjects should be avoided.

If for any reason a treated subject is withdrawn from study participation, the reason for and date of withdrawal from the study must be recorded. If the reason for withdrawal is an adverse event or a clinically significant abnormal laboratory test result, monitoring will continue until the event has resolved, stabilized, or until the follow-up period is complete.

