	The DSMB will be unblinded in order to assess the safety of investigational product (IP).
	The TEC performing adjudication of post-treatment interventions at the treated disc and relationship of adverse events to the product or procedure will be blinded to treatment assignment.
	When the unblinded statistical analyses are conducted at the primary safety and efficacy evaluation (the 24-month safety and efficacy evaluation period), study subjects, as well as site personnel responsible for subject care and assessment, radiographic reviewers and TEC members, will continue to be blinded until completion of the study at 36 months post- treatment.
	An unblinded statistician will conduct the specified interim analyses and only the information prescribed in the SAP will be provided so as to maintain the blind.
Duration of	This is a one-time treatment administration.
Treatment	
Follow up	All subjects will be followed for 36 months post-treatment. Subjects will
Schedule	be evaluated at baseline, treatment day (Day 0), as well as Study Visits 3,
	4, 5, 6, 7, 8, and 9 (corresponding to 1, 3, 6, 12, 18, 24, and 36 months
	post-treatment). The primary analysis of safety and efficacy will be assessed at Visit 8 (24 months post treatment). A longer term follow up
	assessed at Visit 8 (24 months post-treatment). A longer-term follow-up of safety and efficacy will be assessed at Visit 9 (36 months post-
	treatment).
Data & Safety	A DSMB will meet on a regular basis and ad-hoc, as needed, to review
Data & Salety	A DSIMB will meet on a regular basis and au-noe, as needed, to review

[figure not shown]
Monitoring	safety, enrollment progress, and any other pertinent information. The
Board	DSMB will consist of an independent multi-disciplinary group. Based on
	its findings, the DSMB will make recommendations regarding study
	continuation, enrollment and/or study modification(s).
Post-Treatment	Surgical and injection interventions should be avoided through at least
Interventions	the 24 month primary endpoint follow-up. Surgical and injection
	interventions should only be undertaken if the subject's pain, measured by
	VAS, and function, measured by ODI, are not improved compared to the
	baseline values since an intervention could confound the efficacy
	assessments and would classify a subject as a treatment failure.
	For any subjects who are planning any post-treatment intervention during
	the course of the study, every effort should be made to schedule an

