4.6 Withdrawal Procedure

When a subject withdraws from the study or if a subject is withdrawn by the investigator, all assessments normally required at the completion of the study will be obtained, where possible. All details available will be reported and recorded. If the reason for removal of a subject from the study is an adverse event, intercurrent illness, surgical intervention or an abnormal laboratory value considered a clinically significant abnormality, i.e., requiring medical intervention or treatment, the specific event will also be recorded. All AEs are intended to be followed through until resolved or stabilized or until the follow-up period is complete.

Case report forms are required for all subjects who are screened. Subjects who sign an informed consent and undergo any procedures for the study, including those who are subsequently excluded or withdrawn from the study before randomization will be documented on the site's screening log. Whenever possible, all sections of the screening worksheets and relevant case report forms, up to the time of withdrawal, should be completed. If applicable, efforts should be made to obtain complete information regarding safety.

If during the course of the study a subject chooses to revoke his/her written authorization for the use and disclosure of personal health information (PHI; per HIPAA privacy ruling or other country and/or region specific law), the subject will then be withdrawn from the study as well (i.e., participation in the MSB-DR003 study is contingent upon an "active" written PHI use, collection, and disclosure authorization) and only safety data will be collected as required by applicable laws. PHI collected prior to the date that the subject revokes his/her written authorization may still be used. If a subject decides to withdraw from the study, he/she should be asked if he/she can still be contacted for further information. The outcome of that discussion should be documented in the medical records.

If a subject decides to withdraw or is withdrawn from the study, the investigator will promptly notify the blinded CRA, or designee, and the reason for and date of withdrawal from study must be recorded.

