All pregnancies that occur during the study are to be reported within 24 hours to the individual identified in the clinical study personnel contact information section of this protocol, and the investigator must provide sponsor or designee, by facsimile, a signed pregnancy tracking form. If a subject becomes pregnant during the study, the subject will remain in the study and only the requirement for radiation (x-ray or MRI) should be removed. All subjects who become pregnant will be monitored to the completion or termination of the pregnancy, including perinatal and neonatal outcome. Monitoring of the subject should continue until conclusion of the pregnancy. If the pregnancy is associated with an SAE (e.g., hemorrhage, spontaneous abortion), in addition to the Pregnancy Form, a separate SAE form must be provided as described in Section 8.1.

If a subject becomes pregnant during the study, the subject will remain in the study and only the requirement for radiation (x-ray or MRI) should be removed.

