Any subject that is missing one or more components in an endpoint (e.g. VAS in the primary endpoint) at a visit will be considered a non-responder at that visit if any available component of the endpoint indicates that the subject is a non-responder (even if all components of the endpoint are not available). If none of the available components impose non-response, the outcome will be considered missing and will be handled according to the proposed methodology described below.

Assumptions regarding responder analyses include the following:

- If the subject does not meet the criteria of either pain or function at either Visit 6 or Visit 8, the subject will be considered a non-responder.
- If the subject meets the pain and function improvement criteria at both Visit 6 and Visit 8, and has no post-treatment intervention as of the date of Visit 8, the subject will be considered a responder.

- Any subject that is a non-responder on one of the two primary study visits (Visit 6 or Visit 8) but has a missing outcome for the other study visit is deemed a non-responder and not considered to have a missing outcome for the primary analysis.
- If a subject does not have a minimum of a visit at 3-months (Study Visit 4) they will be considered a non-responder.
- Any subject that has a minimum of 3-months data (Study Visit 4) but is missing one or both of the two primary study visits, will have their outcome multiply imputed based on their available information. Separate models will be constructed for
 - Subjects that are missing one of the two primary study visits (Visit 6 or Visit 8) but not both;
 - \circ Subjects that are missing both of the primary study visits.

A detailed description of the statistical methodology for multiple imputation of missing data for responder analyses can be found in the SAP.

For subjects who have a post-treatment interventional procedure at the treated level, the analyses of continuous and categorical efficacy variables will include only data collected before the post-treatment adjudicated intervention.

MMRM will be used for the analysis of over time of quantitative variables and missing data will not be imputed.

The SAP provides additional details regarding methods for handling missing data.

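### Sections 4.5 and 4.6 let the investigator end follow-up of subjects already injected, so Month 12 and 24 outcomes that could be observed may be imputed or assigned instead

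*Combined protocol and SAP*

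**What the plan says.** The Duration of Treatment entry in the synopsis reads: "This is a one-time treatment administration". Section 4.5 nevertheless gives a broad power of removal: "The investigator has the right to withdraw subjects from the study in the event of intercurrent illness, adverse events, administrative, or other reasons". The object of the sentence is the study, not treatment. Section 4.6 adds further grounds through a recording rule that begins: "If the reason for removal of a subject from the study is an adverse event, intercurrent illness, surgical intervention or an abnormal laboratory value".

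The same sections contain some protection. Section 4.5 warns that too many withdrawals could make the study uninterpretable and says that "unnecessary withdrawal of subjects should be avoided". Section 4.6 provides that on withdrawal "all assessments normally required at the completion of the study will be obtained, where possible". Adverse events are to be followed until they resolve or stabilise, or until the follow-up period ends. A subject who chooses to withdraw is to be asked about later contact.

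For pregnancy the protocol takes a different line. Section 8.2, like the eligibility criteria in 4.2.1 and 4.2.2, says that "the subject will remain in the study and only the requirement for radiation (x-ray or MRI) should be removed".

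On the analysis side, Section 9.3.2 makes ITT the primary set. Section 9.4.1 defines the primary endpoint on in-clinic VAS and ODI at Visits 6 and 8. Section 9.9 treats the data as missing if those in-clinic assessments are unavailable. A subject who has Visit 4 but lacks one or both primary visits "will have their outcome multiply imputed based on their available information".

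**The concern.** In a repeat-dose trial, investigator withdrawal may be needed to stop dosing. Here nothing is left to stop once the injection has been given. What ends is the scheduled collection of pain, function, intervention and long-term safety data.

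The listed reasons are not neutral. Subjects removed for an adverse event or illness may well have a different prognosis from those who stay. Where such a subject would have attended Months 12 and 24, a discretionary act replaces an observable ITT outcome with a modelled or assigned one, and the timing of the act decides which.

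Two other analyses are touched. Time to first intervention (Section 9.6.3) censors withdrawn subjects at the last performed visit, so removal linked to worsening could be informative censoring. Safety follow-up is planned to 36 months, and Section 1.7.5 says the long-term effects of the injection are unknown. Removed subjects drop out of that record.

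**Working it through.** The point is mainly textual, and the visible text gives no withdrawal rate to reproduce. The check has three steps.

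**1. Do the safeguards secure Visits 6 and 8?**
- The advice against unnecessary withdrawal does not narrow the listed reasons.
- The exit assessment is a single set, where possible. Visits 6 and 8 are 12 months apart with windows of ±60 days (Table 3), so one exit assessment can serve at most one of them, and only if it happens to fall in a window.
- Monitoring after withdrawal follows the event, not VAS and ODI.
- The question about later contact is written for subjects who decide to withdraw, not for those whom the investigator removes.

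None of the four requires in-clinic VAS and ODI at Months 12 and 24.

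**2. What does Section 9.9 do with an injected subject who is withdrawn?**
- No Visit 4: non-responder.
- Listed treated-level intervention recorded by Visit 8: non-responder, whatever else is missing.
- Any available component failed at Visit 6 or Visit 8: non-responder.
- Visit 4 present, Visits 6 and 8 both missing, no failure or intervention recorded: multiply imputed.
- Visit 4 present, success at one primary visit, the other missing, no intervention recorded: multiply imputed under a separate model.
- Withdrawn after Visit 8: primary outcome already settled; only longer-term follow-up is lost.

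The exposed groups are therefore the first, where failure is assigned, and the two imputed ones.

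**3. How large could the effect be?** Inputs from the documents: about 120 subjects per arm (Section 3.1) and a Phase 1b/2 success rate of 44.4% at 6 million cells (Section 1.6.3), rounded to 44% as the upper imputed rate. Assumed: share removed and then imputed 3%, 5% or 8%; lower imputed rate 30%; true success in removed subjects 5% to 10%.

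Shift in one arm's rate = share removed × (imputed rate − true rate). The gap runs from 0.30 − 0.10 = 0.20 to 0.44 − 0.05 = 0.39.
- 3%: 0.03 × 0.20 = 0.6 points to 0.03 × 0.39 = 1.2 points
- 5% (6 of 120): 0.05 × 0.20 = 1.0 point to 0.05 × 0.39 = 1.95 points
- 8%: 0.08 × 0.20 = 1.6 points to 0.08 × 0.39 = 3.1 points

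The extreme bound at 5% is 6/120 = 5 points on that arm's rate.

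With equal shares and equal gaps in the active and saline arms, the shifts cancel in the difference. With 5% removed in one arm, 3% in the other and the same gap, the difference moves by 0.02 × 0.20 = 0.4 to 0.02 × 0.39 = 0.8 points.

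**The case against.** The strongest reply is that the text grants a right and mandates nothing. It already discourages needless withdrawal, requires reasons to be documented, and asks for an exit assessment and adverse event follow-up. That is fair, and it keeps the point modest. It does not close the gap, because no provision asks for the primary assessments after an investigator's withdrawal.

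Four stronger readings are tempting, and the documents do not support them.
- *Leaving the study ends no exposure at all.* Participation carries X-rays at seven post-treatment visits, MRI and blood sampling; Section 1.7.7 puts all study imaging at about 19.2 mSv. The accurate statement is that no study treatment is stopped. The imaging burden is a reason to waive imaging, as for pregnancy, rather than to lose VAS and ODI.
- *Surgery makes the primary outcome missing.* Section 4.5 does not name surgery, and 4.6 names it only in a recording rule. A listed procedure at the treated level by Visit 8 is non-response under 9.9. For those subjects the loss is safety follow-up.
- *After removal only the triggering event is followed.* Section 4.6 also asks for the exit assessment, follow-up of all adverse events and, if applicable, efforts to complete the safety information.
- *Every removal after Visit 4 is imputed.* Only those with no recorded failure or treated-level intervention are.

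The size is also open to challenge. Section 9.9 imputes from each subject's available information, which could include earlier visits and perhaps the exit scores. The model is left to the SAP, and its detail is not in the visible text. The 20 to 39 point gap is therefore an assumption about the model as well as about the subjects.

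**Conclusion.** The point holds as a low-cost improvement to the design. Sections 4.5 and 4.6 permit removal from follow-up for reasons that, after a single injection, need not end it, and the existing safeguards do not protect the in-clinic Visit 6 and 8 assessments. The result is avoidable missing or assigned primary outcomes, and thinner safety data to 36 months.

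The size is undetermined. The figure of 1 to 2 points on one arm rests on an assumed 5% removal share and an assumed imputation gap. A reader might infer that the treatment comparison is biased by that amount, or in favour of the active arms. The documents do not support this: bias in the comparison arises only if removals, or the removed subjects' prognosis relative to what is imputed, differ by arm, and nothing in the text shows that they do.

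**What to change.** Amend Sections 4.5 and 4.6 for subjects who have been injected and still consent:
- An adverse event, intercurrent illness, surgery, laboratory abnormality or administrative problem does not end study follow-up.
- The subject keeps the scheduled visits, with in-clinic VAS and ODI at Visits 6 and 8 as the default, and follow-up of interventions and adverse events through Visit 9.
- Any assessment unsuitable for the subject's health, such as imaging, is waived, on the model already used for pregnancy.
- Telephone contact is a fallback for interventions and adverse events only. It cannot rescue VAS or ODI, because 9.9 counts scores not taken in clinic as missing.
- Withdrawal of consent, revoked authorization to use health information (4.6), death and loss to follow-up remain exit routes. Withdrawals before injection are unaffected.

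The cost is amendment wording, site training and a few extra visits for subjects who would otherwise have been removed.
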